## 9.2 SUBJECT SUB-GROUP ASSIGNMENT

A total of 36 subjects with infiltrative/morpheaform, nodular, or superficial BCC will be enrolled in the study. For patients with multiple BCC lesions, one “target lesion” will be identified and used for subject sub-group assignment for the purposes of enrollment and followed for primary endpoint analysis. For scientific purposes, data from BCC tumors other than “target lesion” will also be collected. The lesion(s) biopsied at Screening Visit will be reviewed and each subject will be assigned to a subtype group as detailed below and in Figure 5.

**Step 1.** Infiltrative/morpheaform subtype lesion will be given priority in subject sub-group assignment.

**Step 2.** If a potential subject does not have a possible target lesion that is infiltrative/morpheaform subtype and has a superficial BCC, then the subject will be assigned to the superficial BCC subtype group.

**Step 3.** If no infiltrative/morpheaform BCC or superficial BCC are identified, then nodular BCC will be eligible for enrollment.

[figure not shown]

Figure 5. Target Lesion Assignment Algorithm

If there are two lesions that may be eligible for target lesion assignment based on histologic subtype, then the lesion with larger clinical dimensions will be designated the “target lesion”. See Appendix 10, Target Lesion Assignment Examples for more information.

This “Target Lesion Assignment Algorithm” will continue in this fashion until any two of the subtype groups reaches 26. This is to ensure that each subgroup has at least 10 subjects. At this point, subjects enrolled must have at least 1 BCC of the remaining subtype group.

## 9.3 PARAMETERS TO BE MEASURED:

### 9.3.1 Primary Endpoints

Efficacy of vismodegib in treatment of target lesion(s) by clinical and histologic response evaluation.

#### 9.3.1.1 Clinical Response

- Comparison of number of target lesions in each of the following groups:
  - Complete response, partial response, stable disease, or disease progression as defined above

- Overall response rate and best overall response rate
- Comparison of maximum diameter and lesion area of target lesion(s) post-biopsy and at End of Treatment visit
- Comparison of dimensions of tumor within “debulking” specimen at surgery visit with dimensions of pre-biopsy tumor

#### 9.3.1.2 **Histologic response (at Week 12 and Week 24/Surgical Visit)**

- **Residual tumor**
  - Evidence of any histologic change in residual tumor tissue compared to pre-treatment biopsy specimens
  - Estimate of changes in cellular density and composition at Week 12 and Week 24/Surgical Visit
- **Area of Tumor Clearance**
  - Assessment of histologic clearance in areas of apparent clinical tumor clearance at Week 12 and Week 24, and/or Surgical Visit
- Comparison of deepest “invasion index” on biopsy specimen, at Week 12 biopsy, and “debulking” specimen or “tumor margins” specimen” at Surgery visit
- Histologic subtypes observed on pathologic specimens (Screening visit and Week 12 and Surgical excision specimen) Location and depth of specific tumor cells of each histologic subtype on biopsy, week 12 biopsy, and Surgical excision specimens
- Percentage of each histologic subtype in tumor specimen on biopsy, Week 12 biopsy and surgical excision specimens

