Adjuvant therapies aiding in the removal of primary or recurrent tumors could lessen the risk of cosmetic disfigurement by decreasing tumor burden prior to surgery. Topical therapies, such as imiquimod, have been investigated in the past for this purpose. They are not widely used due to concern that the variable penetration of topical therapy may lead to noncontiguous response, leading the clinician to incorrectly believe that the tumor has been completely cleared. (Harting et al 2007) An oral agent, that hypothetically would be distributed to the tumor uniformly, may be better suited for neoadjuvant treatment of BCC prior to surgery. In fact, in selected lesions, oral treatment could possibly even lead to complete eradication of tumor tissue, thereby eliminating the need for surgery altogether. Vismodegib is an orally delivered small Hedgehog pathway inhibitor (HPI) that shows promise in the management of BCC. Vismodegib was granted priority review and was recently approved by the U. S. Food and Drug Administration for the treatment of adults with metastatic basal cell carcinoma or with locally advanced basal cell carcinoma that has recurred following surgery or who are not candidates for surgery, and who are not candidates for radiation.

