Histologic features are well known to impact tumor biologic behavior and response to treatment. Treatment options for BCC are often curative when considering clinical and histologic features, the latter a more powerful prognostic factor with laBCCs and hrBCCs. (Walling et al 2004) For example, it is well recognized that infiltrative/morpheaform tumors are associated with increased rates of recurrence and poorer prognosis since their tumor characteristics make it difficult to obtain clear margins during surgery. (Walling et al 2004) These BCC subtypes frequently have tumor nests outside of the tumor bulk. During surgery, tumor remnants may go undetected by conventional means and continue to grow. If a histological response to vismodegib in aggressive subtypes can be demonstrated pre-operatively, clinicians may possess greater confidence that all tumor nests have been eradicated and clear margins have been obtained during surgery, leading to improved patient outcomes. Conversely, superficial BCCs are considered to have non-aggressive tumor behavior and are also more likely than other subtypes to be located on the low-risk locations of the trunk and extremities. (Weedon 2009) These tumors, which typically undergo simple excisions, nonetheless can require significant circumferential margins of normal tissue to ensure complete removal, again impacting cosmesis, function and or cost.

It is unknown if BCC histologic subtype impacts tumor response to vismodegib. Data from previous studies, where inclusion was open to all subtypes of basal cell skin cancer, is predominantly based on nodular subtype. Most currently recruiting studies investigating vismodegib in BCC do not specify a tumor subtype for inclusion, but if one is specified for inclusion, it is nodular subtype only. (ClinicalTrials.gov Identifier NCT01201915) No previous or ongoing studies have stipulated inclusion of other histological subtypes of BCC.

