## 3. STUDY DESIGN

This is a Phase 2B two-site, open-label, nonrandomized 24-week study of the efficacy and safety of vismodegib (150 mg PO daily) in subjects with high risk and/or locally advanced basal cell carcinoma. A total of 36 subjects with infiltrative/morpheaform, nodular, or superficial BCC will be enrolled in the study. Each subtype group will have a minimum of 10 subjects. No group will have more than 16 subjects.

At Treatment Initiation Visit (Baseline/Day 1), eligible subjects will begin a 24-week treatment regimen with vismodegib 150 mg daily. Clinical assessments will be performed every 4 weeks during treatment. Intra-treatment tissue histopathologic evaluation will be conducted at Week 12. Subjects will be eligible to discontinue treatment early and enter the Observation period if there is no histologic evidence of tumor on Week 12 pathology specimens. Post-treatment histopathologic evaluation will be performed at Week 24 (End of Treatment visit). Subjects will be eligible to enter the Observation period in lieu of surgery if their target lesion displays complete histologic response on biopsy specimens obtained at Week 24 visit. For subjects with histologic evidence of disease on pathology at Week 24 visit, surgical excision or Mohs surgery on the target lesion will be performed within 4 weeks of the last dose of study drug. Patient Reported Outcomes (PRO) data will be collected at baseline visit, during treatment, end of treatment/early termination visit, surgical visit, and study exit (post-surgery) visit, and at first Observation period visit (when applicable) Safety assessments including adverse event (AE) monitoring and concomitant medications will be performed at each visit.

The rationale for using 24-week treatment schedule was based on previous data from pilot studies. Data from a previous trial of 33 subjects with advanced BCC, demonstrated that 94% (17/18) of responders responded by 24-weeks. (Von Hoff et al 2009) In non-responders, treatment beyond 24 weeks may unnecessarily endanger the patient and allow their basal cell skin cancer to progress potentially negatively affecting clinical outcome.

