#### **Tumors Exhibiting Complete Clinical Response**

For lesions that the investigator has determined to show complete clinical response at Week 12 visit, sampling biopsy will be performed at the farthest edge(s) of pre-biopsy lesion compared to location of initial punch biopsy/biopsies at Pre-study Screening Visit (See Figure 1 A). Up to three 2-mm or three 3-mm punch biopsies will be performed on the area of tumor clearance at Week 12 when possible. Tumor biopsies may comprise no more than 10% of visible lesion seen at screening visit.

[figure not shown]

Figure 1. Site of Week 12 biopsies for tumors with exhibiting complete clinical response.

For lesions that display partial clinical response or stable disease by clinical response evaluation, “Residual Tumor Assessment” and “Area of Tumor Clearance Assessment” will be performed (See Figure 2.).

[figure not shown]

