**6.1.4 End of Treatment visit (Week 24)**

Any unused study drug will be collected.

After 24 weeks of treatment, all subjects will undergo sampling biopsy/biopsies. If residual histologic disease is detected, surgical excision will be performed within 4 weeks of last dose of study drug. If no histologic evidence of disease is observed, subjects will enter the observation period and be followed clinically every 3 months up to one year. (See Appendix 5, Figure 1 and Figure 2.)

Biopsies at Week 24 visit will be performed in similar manner as performed at the Week 12 visit.

For lesions that the investigator has determined to show complete clinical response at Week 24 visit, sampling biopsy will be performed at the farthest edge(s) of pre-biopsy lesion compared to location of initial punch biopsy/biopsies at Pre-study Screening Visit and sites of biopsies performed at Week 24 visit (See Figure 3). Up to three 2-mm or three 3-mm punch biopsies will be performed on the area of tumor clearance at Week 24 when possible. Tumor biopsies may comprise no more than 10% of visible lesion seen at screening visit.

[figure not shown]

Figure 3. Site of biopsies for tumors displaying clinical complete response at Week 24 visit.

For lesions that display partial clinical response or stable disease by clinical response evaluation, “Residual Tumor Assessment” and “Area of Tumor Clearance Assessment” will be performed (See Figure 4)

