#### 6.1.8 **Observation period**

All subjects will be followed for the observation period of 1 year after discontinuation of study medication.

During the observation period the subjects will followed every 3 months for 1 year after last dose.

The following study procedures during observation period:

- Assessment of any changes (deletions, additions, or dose modifications) to medications.
- Complete physical examination including general appearance, skin exam, and visual inspection of target lesion(s) area.
- Vital signs (BP; heart or pulse rate; and oral, tympanic, or temporal temperature).
- Weight and height measurements.
- Urine pregnancy test ( $\alpha$ -hCG) only for women who are of childbearing potential for visits within 7 months of last dose of study drug.
- Photography and measurement of target lesion area
- Adverse Event (AE) Monitoring.
- Reminder to use effective measures to avoid pregnancy (for women who are of child bearing potential for visits within 7 months of last dose of study drug).
- PRO questionnaires will be performed by the subject (SKINDEX-16 and Functional Assessment of Cancer Therapy – General (FACT-G) at first visit during Observation period (3 months after discontinuing treatment).

If a subject is noted to have a recurrence of target lesion or new lesions suspicious for BCCs on any part of the body, biopsy will be performed to confirm diagnosis. If pathology is consistent with basal cell carcinoma, the subject will exit the Observation period and all treatment options

will be discussed with the subject. If Mohs micrographic surgery is determined to be the best therapeutic option, surgical excision and study procedures will be performed as described in Section 6.1.6.

Subjects who underwent surgical excision of the target lesion may elect to be followed by phone contact every 3 months to provide information on the status of the surgical site and occurrence of any adverse events.

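### In subjects who skip surgery, punch-negative clearance is never checked on whole tissue, and the one-year recurrence data enter no endpoint or analysis

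*Combined protocol and SAP*

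**What the plan says.** The primary endpoint in section 9.3.1.2 includes "Assessment of histologic clearance in areas of apparent clinical tumor clearance at Week 12 and Week 24, and/or Surgical Visit". Section 9.3.3.1.2 analyzes it by chi-square, overall and by subtype.

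For lesions in complete clinical response, section 6.1.3 states: "Up to three 2-mm or three 3-mm punch biopsies will be performed on the area of tumor clearance at Week 12 when possible". It adds a cap: "Tumor biopsies may comprise no more than 10% of visible lesion seen at screening visit". Section 6.1.4 repeats both rules at Week 24. For partial response or stable disease, the residual tumor is punched directly under the same percentage cap, and the cleared area is punched with no cap stated.

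On the consequence, section 3 says: "Subjects will be eligible to enter the Observation period in lieu of surgery if their target lesion displays complete histologic response on biopsy specimens". Section 6.1.4 says: "If no histologic evidence of disease is observed, subjects will enter the observation period". Subjects with residual disease at Week 24 have the tumor and its margins excised and examined (6.1.6).

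Section 6.1.8 provides visits every 3 months for one year after the last dose. "If a subject is noted to have a recurrence of target lesion", or a suspicious new lesion anywhere, a biopsy is taken. A confirmed basal cell carcinoma ends observation for that subject.

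**The concern.** Verification runs in one direction only. A positive Week 24 punch leads to excision and examination of the whole specimen. A negative one leads to no further tissue unless a recurrence becomes visible. Missed tumor therefore stays in the numerator of the clearance rate.

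The protocol recognizes this hazard. Section 1.1 explains the limited use of topical treatment by patchy response, "leading the clinician to incorrectly believe that the tumor has been completely cleared". Section 1.2 says of infiltrative/morpheaform tumors: "These BCC subtypes frequently have tumor nests outside of the tumor bulk".

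The study already collects information that bears on the problem, namely biopsy-confirmed recurrence at the target site over a year, but sections 9.3.1 to 9.3.3 never use it. The clearance rate may be overstated, the comparison between subtypes may be distorted, and the suggestion in section 1.1 that oral treatment might spare some patients surgery goes unanalyzed.

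**Working it through.** **1. The plan's own figures.** Section 9.1 gives intervals for response rate only. The Wald formula p ± 1.96·√(p(1−p)/n) reproduces them: 12/16 gives 53.8%–96.2% (stated 54%–96%), and 4/10 gives 9.6%–70.4% (stated 10%–70%). They describe sampling of subjects, not of tissue within a lesion. The documents give no punch miss rate, so steps 4 to 6 rest on assumptions.

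**2. Where each result leads.**

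| Finding | Next step | Whole-tissue check |
|---|---|---|
| Complete clinical response, punches negative, Week 12 | Observation | None |
| Partial response or stable disease, punches negative, Week 12 | Treatment continues, biopsy again at Week 24 | Not yet final |
| Punches negative, Week 24 | Observation | None |
| Punches positive, Week 24 | Excision with margins | Yes |

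Sections 9.3.1 to 9.3.3 list response category, dimensions, histologic change, clearance, invasion index, subtype composition, onset, safety and questionnaires. Target-site recurrence does not appear, and no rule reclassifies a cleared lesion that recurs.

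**3. Tissue sampled** (circular lesion assumed; punch area π·d²/4 = 3.14 mm² for 2 mm and 7.07 mm² for 3 mm).
- 20-mm lesion (314.2 mm²): three 3-mm punches cover 21.2/314.2 = 6.8%; three 2-mm punches cover 3.0%.
- 30-mm lesion (706.9 mm²): 3.0% and 1.3%.
- 10-mm lesion (78.5 mm², cap 7.85 mm²): the cap allows two 2-mm punches or one 3-mm punch.
- 6-mm lesion, the smallest eligible under section 4.1 (28.3 mm², cap 2.83 mm²): one 2-mm punch is already 11.1%, so the cap cannot be met.

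**4. Chance that all punches miss** (assumed random sites; s = share sampled, k = number of point-like nests): (1−s)^k.
- s = 10%: 90%, 73%, 59% and 35% for k = 1, 3, 5 and 10.
- s = 3%: 97%, 91%, 86% and 74%.

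A simulation of three 3-mm punches on a 20-mm lesion gives 92%, 66% and 45% for 1, 5 and 10 nests of radius 0.1 mm, and 78%, 32% and 10% for radius 1 mm. The range is very wide. More nests make a complete miss less likely.

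**5. Effect on the rate.** Let t be true clearance, m the miss rate, and c the share of uncleared lesions that look clear, so that punches are placed blind. Assume punches into visible residual tumor detect it. Observed rate = t + (1−t)·c·m. With assumed t = 40% and m = 50%:
- c = 0.2: 0.40 + 0.60·0.2·0.5 = 46%
- c = 0.5: 55%
- c = 1: 70%

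**6. Effect on the subtype contrast** (c = 1, the most adverse case; all inputs assumed; 75% and 40% are borrowed from the response rates behind section 9.1).

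| True nodular / infiltrative | Miss nodular / infiltrative | Observed | Difference, true → observed |
|---|---|---|---|
| 40 / 40 | 10 / 50 | 46 / 70 | 0 → −24 |
| 40 / 40 | 50 / 50 | 70 / 70 | 0 → 0 |
| 40 / 40 | 50 / 10 | 70 / 46 | 0 → +24 |
| 75 / 40 | 50 / 50 | 87.5 / 70 | 35 → 17.5 |
| 75 / 40 | 10 / 50 | 77.5 / 70 | 35 → 7.5 |
| 75 / 40 | 35 / 90 | 83.75 / 94 | 35 → −10.25 |

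A common miss rate creates no false difference but shrinks a true one by the factor 1 − c·m. A false difference needs unequal miss rates (or an unequal c), and its sign follows whichever group is assumed worse.

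**7. What recurrence data can add.** With no recurrence among n cleared subjects, the one-sided 95% upper bound is 1 − 0.05^(1/n): 53% for n = 4, 35% for n = 7, 22% for n = 12. If 7 of 10 infiltrative subjects were punch-negative (assumed), then 0, 1, 2 or 3 recurrences give sustained clearance of 7/10, 6/10, 5/10 or 4/10, with exact 95% intervals of 35–93%, 26–88%, 19–81% and 12–74%.

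**The case against.** The strongest reply is that blind sampling affects only part of the cohort. Partial-response and stable lesions are punched in visible tumor and, if positive at Week 24, excised with the pre-biopsy area. Week 12 negatives in those groups are biopsied again, and the endpoint wording allows the surgical visit as a source. Complete responders are punched at chosen edge sites, so random placement is only a model. This stands, and it is why step 5 carries the factor c. It does not help a lesion that looks clear and is punch-negative.

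A second reply is scope: section 9.1 calls this a pilot, and the secondary objectives run over 24 weeks. Recurrence within a year may also be regrowth after true clearance, so it cannot reclassify the Week 24 result. This also stands. The added endpoint measures durability and should be described that way.

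A reader might infer from section 1.2 that false clearance is highest in the infiltrative group and that the subtype ranking could reverse. The documents do not support that conclusion. Section 1.2 is qualitative, concerns detection at surgery, and gives no miss rate by subtype. Step 4 shows that wider scatter can lower the chance of a complete miss. In step 6 a reversal appears only with an unsourced pair such as 35% and 90%.

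**Conclusion.** The concern holds for subjects sent to observation instead of surgery. Their clearance rests on up to three small punches, is never checked on whole tissue, and is not revised if biopsy later confirms recurrence at the target site. The error can only inflate the reported clearance rate. Its size cannot be derived from the documents: 46% to 70% in place of 40% is an illustration under an assumed 50% miss rate with c between 0.2 and 1.

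Unequal miss rates by subtype are a risk that section 1.2 suggests, with direction and size unknown. A subtype figure should appear only as a range under stated assumptions. Recurrence data would reduce the problem without removing it. They are few, they depend on a recurrence becoming clinically suspicious, and follow-up ends early when a basal cell carcinoma is confirmed elsewhere. That may happen more often in subjects with Basal Cell Nevus Syndrome, who are eligible.

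**What to change.** 1. In 9.3.1.2, label a negative result 'no tumor on sampling biopsy'.
2. Add to 9.3 and 9.3.3 'sustained clearance without surgery': no tumor on the last on-treatment biopsies and no biopsy-confirmed target-site recurrence through one year. Report it by subtype over all subjects with exact 95% intervals. Excised subjects count as not achieving it. For subjects with incomplete follow-up, show both extremes (all sustained, all recurred).
3. Report time to target-site recurrence by Kaplan-Meier among subjects who skipped surgery, censoring those who leave observation for a carcinoma elsewhere. Fix the window: section 6.1.8 says one year, but the last visit in Appendix 6 falls 48 weeks after treatment (72 − 24 and 60 − 12).
4. State that this measures durability and only partly corrects missed tumor, and give the upper bound when no recurrence is seen.
5. Reconcile the passages that determine who is verified. Sections 1.3 and 6.6.2 imply excision for all treated subjects, while sections 3 and 6.1.4 allow observation instead. Section 6.1.4 requires Week 24 biopsies, which the Appendix 6 flowchart does not show. The 10% cap conflicts with the punch sizes for the smallest eligible lesions.

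The cost is endpoint and analysis wording, plus recording the site of any carcinoma that ends observation. Visits and biopsies are already planned. The downside is a less favorable clearance rate that becomes final a year later.

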#### 9.3.2 **Secondary Endpoints**

##### 9.3.2.1 **Onset of efficacy**

- Onset of efficacy during 24 weeks of treatment by clinical and histologic response
  - Histologic response measured at 12 weeks and after 24 weeks of treatment
- Interval to best overall response during 24 weeks of treatment by clinical response

##### 9.3.2.2 **Safety and Tolerability**

Monitoring of adverse effects, onset of specific adverse effects and adverse effects that lead to early termination of treatment.

##### 9.3.2.3 **Patient Reported Outcomes/Quality of Life**

Evaluation of patient reported outcome (PRO) measures before, during 24 weeks of treatment with vismodegib through SKINDEX-16 and FACT-G questionnaires. (See Appendix VI and VIII.)

#### 9.3.3 **Efficacy Analysis**

##### 9.3.3.1 **Analysis of Primary Endpoints**

#### 9.3.3.1.1 **Clinical Response**

Comparison of dimensions of tumor within debulk specimen at surgery visit with dimensions of post-biopsy tumor as drawn on template at screening visit will be assessed by a t-test for independent samples.

Sub-group analyses by histologic subtype will be conducted by demographic factors including: gender, race, and anatomic location of target lesion will also assessed for any independent association with clinical response. Statistical significance was defined by alpha 0.05. All analysis was performed using SPSS (PASW) version 18.

Analysis of the following subgroups will be performed:

- Nonaggressive subtypes vs. Aggressive subtypes
- Clinical subtypes (infiltrative/morpheaform, nodular, and superficial)

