# 1. **BACKGROUND INFORMATION**

## 1.1 **INTRODUCTION**

Basal cell carcinoma (BCC) is the most common type of skin cancer, with almost 3 million cases diagnosed each year in the United States. (Skin Cancer Foundation 2011, Rogers et al 2010) The incidence of BCC is increasing 10% each year worldwide and its prevalence is expected to equal that of all other cancers combined in the near future. (Madan et al 2010)

Though extremely rare, some patients have progressive mutilating metastatic BCC (mBCC) or locally advanced BCC (laBCC), which can be fatal. Most BCCs are not life-threatening, but they are still quite morbid as they commonly occur on the head and neck. Some BCC lesions grow very quickly and are associated with poorer outcomes. Features of these ‘high risk’ BCC (hrBCC) lesions were defined by the National Comprehensive Cancer Network (NCCN) and this hrBCC cohort was highlighted as one of particular concern. (See Appendix 1, NCCN 2011). Since hrBCC tumors are much more common, they actually represent a much bigger public health problem than mBCC or laBCC.

Due to its superior cure rate, Mohs micrographic surgery (MMS) is widely accepted as the gold standard for treatment for the majority of BCC tumors, especially laBCC and hrBCC. (Mikhail and Mohs 1993, NCCN 2011) Even with the utilization of the Mohs tissue preservation technique, surgery can be quite extensive resulting in significant disfigurement, depending on the size and anatomic location of the lesion.

While size of tumor is a predictive factor of patient outcomes, visual examination can frequently be deceiving and local microscopic invasion may be much more extensive than initially thought. In some cases, tumor seen at the skin surface may only represent one fifth of its microscopic spread. (Batra and Kelley 2004) Since many tumors exhibit significant subclinical extension, the resulting surgical defect after tumor clearance can be considerably larger than the presenting lesion, often necessitating complex, costly, and time-consuming repairs, compromising the final cosmetic appearance or function.

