#### 6.1.1.1 **Target lesion selection**

- If multiple lesions are deemed to be suspicious for basal cell skin cancer on visual inspection, up to 4 lesions will be considered for investigation and designated "potential target lesions". Potential target lesion(s) will be selected at clinician discretion using clinical and dermoscopic findings and in consideration of patient preference.
- Measurement pre- and post-biopsy and high resolution digital photography of potential target lesion(s).

- Template map drawing of clinically evident tumor margins and local landmarks using a permanent marker on a clear plastic overlay.
- To confirm diagnosis of BCC and to designate histologic subtype, up to three representative 2-mm or three representative 3-mm punch biopsies will be performed on each potential target lesion.
  - Skin biopsies performed at Pre-study Screening visit will comprise no more than 10% of visible lesion surface area.
  - Skin biopsies must be performed at least 1 mm from peripheral margin of visible lesion.
- Biopsy of each potential target lesion will be performed in area that clinically appears to be thickest by inspection at palpation. If the potential target lesion appears to be homogenous, the biopsy will be performed at the center of the lesion.
- Post-biopsy pre-treatment lesion area will also be recorded and template drawn.

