## 6.2 METHODS OF ASSESSMENT

### 6.2.1 Measurement of Target Tumor

At the treatment initiation visit, the baseline size of the target tumor will be determined by measuring the 2 largest perpendicular diameters of the target tumor. Target tumor size will be measured at each visit

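### The one test named for clinical response compares a visible skin outline with tumor found inside excised tissue, so its result cannot be read as drug-induced size change and may be distorted differently by subtype

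*Combined protocol and SAP*

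**What the plan says.** Section 9.3.3.1.1 (Clinical Response) names a single test. It is a "Comparison of dimensions of tumor within debulk specimen at surgery visit with dimensions of post-biopsy tumor as drawn on template at screening visit", and the method is an independent-samples t-test. The same section states "Statistical significance was defined by alpha 0.05" and plans analyses by histologic subtype.

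The two sides of the comparison are defined elsewhere:

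- **Baseline.** Section 6.1.1.1 calls for a "Template map drawing of clinically evident tumor margins and local landmarks using a permanent marker on a clear plastic overlay", redrawn after the screening biopsy.
- **Outcome.** Section 6.1.6 defines the debulking specimen as excised known tumor that takes in at least the pre-biopsy area. It sets no outer limit. Tissue taken beyond it becomes a separate tumor margins specimen. Lesions in clinical complete response with residual disease on biopsy follow another rule: their debulk is set by the area of tumor seen on histology. Section 6.3.4 sends both specimens to pathologic evaluation.

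On how visible and microscopic extent relate, Section 1.1 says that in some cases "tumor seen at the skin surface may only represent one fifth of its microscopic spread". Of infiltrative and morpheaform tumors, Section 1.2 says "These BCC subtypes frequently have tumor nests outside of the tumor bulk". Table 1 describes nodular nests as well circumscribed.

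Section 9.3.1.1 also lists, as a primary endpoint, the target lesion's maximum diameter and area after biopsy against the same measures at End of Treatment. Section 6.2.1 supports this: "Target tumor size will be measured at each visit". Section 9.3.3.1.1 names no test for that endpoint.

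**The concern.** A before-after difference measures change only if the same quantity is measured both times. Here the earlier measure is what the clinician can see on the skin, and the later one is tumor located within excised tissue. Subclinical extension present before treatment is left out of the baseline but can enter the outcome. Tumor in the margins specimen enters neither. No section says how dimensions in the specimen are measured or made comparable with the tracing.

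The primary objective (Section 2.1) is to compare efficacy across subtypes. On the protocol's own description, extension beyond the main mass differs by subtype. The mismatch can therefore create or hide a subtype difference in this analysis. Pairing the data, or settling on one baseline, would not remove it.

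**Working it through.** **Planning figures.** Section 9.1 gives confidence intervals for response rates only. They reproduce as Wald intervals, p ± 1.96 × sqrt(p(1-p)/n):

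- n = 16, p = 0.75: 0.75 ± 0.212, or 53.8% to 96.2% (stated: 54%-96%).
- n = 10, p = 0.40 (midpoint of the stated interval): 0.40 ± 0.304, or 9.6% to 70.4% (stated: 10%-70%).

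No power or precision is stated for the dimension test.

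**Model of the named comparison.** All values below are assumptions, because the documents give no ratio by subtype.

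- k = microscopic diameter divided by visible diameter before treatment.
- s = true proportional reduction in diameter, assumed equal for visible and subclinical tumor.
- c = diameter of the debulk divided by the visible outline.
- Apparent change = min(k(1-s), c) - 1.

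The one-fifth figure in Section 1.1 has no stated scale. Read as a length, the extreme k is 5; read as an area, it is sqrt(5) = 2.24. For partial response and stable disease, Section 6.1.6 makes c at least about 1 but sets no maximum.

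**Simulation.** 4,000 runs per scenario; groups of 10 infiltrative/morpheaform, 16 nodular and 10 superficial; mean visible diameter 20 mm, CV 50%, 10% measurement error, two-sided 5% tests. All 36 subjects are given a specimen. The paired and between-subtype tests use each subject's log ratio. Triples are in the order infiltrative, nodular, superficial.

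| True change | k | c | Apparent change | Named t-test rejects | Paired test rejects | Between-subtype test rejects |
|---|---|---|---|---|---|---|
| None | 1.0 / 1.0 / 1.0 (like for like) | no limit | about 0% in each | 0.0% | 5.0% | 5.6% |
| None | 1.5 / 1.1 / 1.3 | no limit | +50% / +10% / +30% | 47% | 100% | 99.8% |
| None | 1.5 / 1.1 / 1.3 | 1.2 | +20% / +9% / +19% | 0.4% | 100% | 48% |
| None | 1.5 / 1.1 / 1.3 | 1.0 | 0% / -1% / 0% | 0.0% | 6.1% | 5.4% |
| None | 2.24 / 1.1 / 1.3 | no limit | +124% / +10% / +30% | 98% | 100% | 100% |
| -33% in all | 1.5 / 1.0 / 1.0 | no limit | +0.6% / -33% / -33% | 69.5% | 100% | 100% |

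The last row can be checked by hand: 1.5 × 0.67 - 1 = +0.5% for infiltrative tumors, and 0.67 - 1 = -33% for the others.

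**A debulk cut at the outline (c = 1.0).** With no true change, spurious growth disappears. With the true 33% reduction of the last row, infiltrative tumors read min(1.005, 1.0) - 1 = 0% and the others min(0.67, 1.0) - 1 = -33%. A tight debulk removes apparent growth, but under these assumptions it leaves the false subtype difference.

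**Like-for-like measurement.** With the visible outline used both times and no true change, the paired and between-subtype tests stay near 5%. The independent-samples test rejects 0.0% because it ignores the pairing.

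**The case against.** The strongest reply is that the plan does not depend on this test. Section 9.3.1.1 lists the like-for-like size comparison, and the response categories in Section 6.2.2 are defined by visible or palpable tumor without using the debulk. A reader might infer that clinical response as a whole is compromised. The documents do not support that. The gap is that the one named test is attached to the unlike comparison and none to the like one.

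Nor is the t-test sentence itself a subtype comparison. Section 9.1 calls the study a pilot and justifies group sizes by response-rate intervals. A reader might take this test to be the basis of the primary subtype conclusion; no section says so. What stands is that subtype analyses are planned under the same heading.

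On size, a reader might treat one fifth as an area ratio and conclude that no drug effect could read as 5 × 1 - 1 = +400%. That counts all excised tumor, whereas the test counts only tumor inside the debulk. It also turns an extreme of unstated scale into a range. A reader might also infer that the test would show shrinkage with no drug effect. Uncounted margin tumor makes that conceivable, but the documents give no figure for it; with an assumed ratio of 0.85 in every subtype, the named test rejects only 4% of the time.

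Finally, comparing tumor left at surgery with the presenting lesion suits the aim of reducing tumor burden before surgery (Section 1.1), and visible size misses subclinical residual tumor. Both are fair. They argue for reporting specimen extent, not for treating it as change from the tracing.

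**Conclusion.** The concern holds. As written, the only test named under Clinical Response sets unlike quantities against each other, and the protocol's background explains why they can differ and why the difference may vary by subtype. The result cannot be read as drug-induced size change.

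The size and direction of the distortion cannot be computed from the documents. They depend on the ratio of microscopic to visible extent in each subtype and on how far the debulk extends past the outline. The figures above show the mechanism under assumed ratios and do not estimate the bias in this trial. The study can run as designed, but the analysis wording should change before this comparison is used to describe efficacy.

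**What to change.** In Section 9.3.3.1.1:

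1. Replace the named test with a within-subject (paired) analysis of the endpoint already in Section 9.3.1.1: clinically measured maximum diameter and lesion area, post-biopsy baseline against End of Treatment, overall and by subtype. For subjects who stop early, use the last on-treatment visit.
2. State which post-biopsy measurement is the baseline: the one at screening, or the treatment initiation measurement that Section 6.2.1 calls baseline. Section 9.3.1.1 gives the debulk comparison a pre-biopsy baseline and Section 9.3.3.1.1 a post-biopsy one, so this needs saying once.
3. Report tumor extent in the debulk and margins specimens together as a descriptive measure of residual disease, not as change from the template.
4. Align the lesion-measurement rows of the Appendix 6 flowchart, marked at screening only, with the interval-visit procedures in Section 6.1.2 and with Section 6.2.1, which require measurement at each visit.

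The cost is wording: the measurements are already required, and the margin map is already scheduled through Week 24. The change also brings in subjects without residual disease, who under Section 6.1.4 go to observation and have no debulk specimen. The drawback is that clinical size does not capture subclinical residual tumor; the histologic endpoints and the descriptive specimen report cover that.
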